7.2.2. Adverse Event Summaries

An overall summary of AEs by dose level will include the following:

- Number (%) of participants reporting any TEAEs
- Number (%) of participants reporting any serious TEAEs
- Number (%) of participants reporting any Grade 3 or higher TEAEs
- Number (%) of participants who had any TEAEs related to pemigatinib
- Number (%) of participants who temporarily interrupted pemigatinib because of TEAEs
- Number (%) of participants who permanently discontinued from pemigatinib because of TEAEs
- Number (%) of participants who had pemigatinib dose reductions because of TEAEs
- Number (%) of participants who had any TEAEs with a fatal outcome

The following summaries will be produced by MedDRA term (if 10 or fewer participants appear in a table, a listing may be appropriate):

- Summary of TEAEs by MedDRA SOC and PT
- Summary of TEAEs by MedDRA PT in decreasing order of frequency
- Summary of Grade 3 or higher TEAEs by MedDRA SOC and PT
- Summary of serious TEAEs by MedDRA SOC and PT
- Summary of TEAEs with a fatal outcome by MedDRA SOC and PT
- Summary of pemigatinib treatment-related serious TEAEs by MedDRA SOC and PT
- Summary of TEAEs leading to pemigatinib dose reduction by MedDRA SOC and PT
- Summary of TEAEs leading to pemigatinib dose interruption by MedDRA SOC and PT
- Summary of TEAEs leading to discontinuation of pemigatinib by MedDRA SOC and PT

Listings will be provided for all AEs, SAEs, AEs of Grade 3 and higher, treatment-related AEs, fatal AEs, and AEs leading to interruption, reduction, or discontinuation of study drug. All listings will be presented for the safety population.

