2.3.1. Benefit/Risk Assessment During the COVID-19 Pandemic

Participants to be enrolled into this study have recurrent advanced or metastatic endometrial cancer and may be at higher risk for complications if they contract COVID-19. In this Phase 2 study population, standard of care therapy options for advanced or metastatic endometrial cancer that progressed on or following platinum-based chemotherapy are limited. A European Society for Medical Oncology multidisciplinary panel highlighted the importance of clinical cancer research to find better therapeutic options for participants even during the pandemic, including potential investigational therapies similar to immunotherapy with a known survival benefit ([Curigliano et al 2020](#)). Preliminary data released based on real-world data indicate that the use of immunotherapy either alone or in combination with chemotherapy does not appear to increase the risk of hospitalization in patients with COVID-19 infection ([Horn et al 2020](#)) or cause an increased risk of mortality ([Lee et al 2020](#)). The effects of immune checkpoint inhibitors on SARS-CoV-2 infection are currently unknown. However, at early stages of SARS-CoV-2 infection, CD8+ T-cell exhaustion and PD-1 upregulation have been observed ([Riva et al 2020](#), [Zheng et al 2020](#)). Those findings suggest that immune checkpoint inhibitors may ameliorate the early phase of COVID-19 through the reactivation of T cells expressing PD-1 ([Maio et al 2020](#)). Conversely, potential risks of cytokine release syndrome, pneumonitis, or myocarditis related to immune checkpoint inhibitor therapy may represent a clinical issue and impact a course of COVID-19 ([Maio et al 2020](#), [Sullivan et al 2020](#)). Considering the critical medical need for alternative therapies in the setting of recurrent advanced/metastatic endometrial cancer and the importance of continuing clinical cancer research even during the pandemic and taking into account the lack of conclusive clinical data on the impact of immune checkpoint inhibitor therapy on the course of COVID-19, the sponsor is implementing additional guidance for participation in this study in the context of the COVID-19 pandemic and study treatment management in the event of SARS-CoV-2 infection (see [Appendix C](#)).

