- The seriousness, as per the SAE definition provided in Section 9.2.
- The action taken with regard to the event. Note: If an AE is treated with a concomitant medication or nondrug therapy, this action should be recorded on the Adverse Event Form and the treatment should be specified on the appropriate eCRF (eg, Prior/Concomitant Medications).

Assessment of Intensity

The severity of AEs will be assessed using CTCAE v5.0 Grades 1 through 5. If an event is not classified by CTCAE, the severity of the AE will be graded according to the scale below to estimate the grade of severity.

The investigator will make an assessment of intensity for each AE and SAE reported during the study and assign it to 1 of the following categories:

- **Grade 1:** Mild; asymptomatic or mild symptoms; clinical or diagnostic observations only; treatment not indicated.
- **Grade 2:** Moderate; minimal, local, or noninvasive treatment indicated; limiting age-appropriate activities of daily living.
- **Grade 3:** Severe or medically significant but not immediately life-threatening; hospitalization or prolongation of hospitalization indicated; disabling; limiting self-care activities of daily living.
- **Grade 4:** Life-threatening consequences; urgent treatment indicated.
- **Grade 5:** Fatal.

Assessment of Causality

- The investigator is obligated to assess the relationship between study treatment and each occurrence of each AE/SAE. If reference therapy is used in combination with an Incyte study drug or if multiple Incyte study drugs are used, then the relationship to each study drug/reference therapy must be assessed.
- A "reasonable possibility" of a relationship conveys that there are medical facts, evidence, and/or arguments to suggest a causal relationship, rather than that a relationship cannot be ruled out.

- The investigator will use clinical judgment to determine the possibility of a relationship.
- The investigator will also consult the RSI in the IB or Product Information for study drug/treatment, or marketed products, respectively, in making his/her assessment.
- Alternative causes, such as underlying or concurrent disease(s), concomitant therapy, and other risk factors, as well as the temporal relationship of the event to study treatment administration, will be considered and investigated.
- For each AE/SAE, the investigator **must** document in the medical notes that he/she has reviewed the AE/SAE and has provided an assessment of causality.

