Table 1:	Objective and Endpoint	6
Table 2:	Statistical Analysis Plan Versions	16

LIST OF FIGURES

Figure 1:	Study Design Schema	8
-----------	---------------------------	---

LIST OF ABBREVIATIONS

Abbreviations and Special Terms	Definition
AE	adverse event
CRF	case report form
CTCAE	Common Terminology Criteria for Adverse Events
eCRF	electronic case report form
FAS	full analysis set
MedDRA	Medical Dictionary for Regulatory Activities
PT	preferred term
QD	once daily
SAE	serious adverse event
SAP	statistical analysis plan
SOC	system organ class
Study treatment	refers to pemigatinib monotherapy or combination therapy with pemigatinib
TEAE	treatment-emergent adverse event
WHO	World Health Organization

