5.2. Treatment Groups

This is an open-label, multicenter, rollover study for participants with advanced malignancies currently enrolled in Incyte-sponsored studies of pemigatinib who are continuing to receive clinical benefit from treatment with pemigatinib (as either monotherapy or in combination therapy).

Participants will be summarized by initially assigned dose level and overall monotherapy total (pemigatinib monotherapy 6 mg QD, pemigatinib monotherapy 9 mg QD, pemigatinib monotherapy 13.5 mg QD, pemigatinib monotherapy total, pemigatinib 9 mg QD + pembrolizumab 200 mg) in this study.

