7.2. Adverse Events

7.2.1. Adverse Event Definitions

Adverse events that are ongoing at the time of rollover from the parent Protocol will be entered on the Adverse Event Form in the eCRF for this study.

A TEAE is any AE either reported for the first time in this Protocol and within 30 days of last dose of study treatment, or any AE ongoing and defined as treatment-emergent from the parent Protocol. Analysis of AEs (as discussed below) will be limited to TEAEs, but data listings will include all AEs regardless of their timing and in relation to study treatment administration. For purposes of analysis, all AEs will be considered TEAEs unless the AE can unequivocally be defined as not treatment-emergent.

Adverse events will be tabulated by MedDRA PT and SOC. Severity of AEs will be graded using the National Cancer Institute CTCAE v5.0. The CTCAE reporting guidelines and grading details are available on the Cancer Therapy Evaluation Program website.

A grading (severity) scale is provided for each AE term. If the toxicity is not included in the CTCAE v5.0 criteria, it will be rated on a scale of 1 to 5 as follows: 1 = mild, 2 = moderate, 3 = severe, 4 = life-threatening, and 5 = fatal. All toxicities will be graded based on the worst level reached, not the level they may have reached if they had not been treated. When the intensity of an AE changes over time for a reporting period (eg, between visits), each change in intensity will be reported as an AE until the event resolves.

The subset of AEs considered by the investigator to be related to study treatment will be considered to be treatment-related AEs. If the investigator does not specify the relationship of the AE to study drug, the AE will be considered to be treatment-related. The incidence of AEs and treatment-related AEs will be tabulated. Serious TEAEs will also be tabulated. In addition, serious TEAEs and serious AEs will be listed.

Any missing data pertaining to date of onset, causality, or severity must be queried for resolution. Unresolved missing causality and severity will be handled according to the following rules:

- An unresolved missing causality will be considered treatment-related.
- An unresolved missing severity will be identified as an unknown severity.

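### The SAP plans no table of TEAEs related to study treatment: its relatedness and action displays cover pemigatinib only, so events tied solely to pembrolizumab are missing from them

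*SAP*

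**What the plan says.** **Definition.** SAP 7.2.1 states: "The subset of AEs considered by the investigator to be related to study treatment will be considered to be treatment-related AEs". The SAP abbreviation list says that study treatment "refers to pemigatinib monotherapy or combination therapy with pemigatinib", and SAP Section 3 counts pembrolizumab and INCMGA00012 (both for INCB 54828-101 only) among the study treatments. SAP 7.2.1 then commits to tabulating how often treatment-related AEs occur.

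**Protocol analysis.** Protocol 10.3.3 asks for TEAE tables by SOC and PT for three sets: all events, related events, and Grade 3 or higher events. It does not restrict the related set to pemigatinib or to serious events. SAP 9.1 records no change to the Protocol-defined analyses.

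**Planned displays.** The overall summary in SAP 7.2.2 has rows for "Number (%) of participants who had any TEAEs related to pemigatinib", "Number (%) of participants who temporarily interrupted pemigatinib because of TEAEs" and "Number (%) of participants who permanently discontinued from pemigatinib because of TEAEs", plus a pemigatinib dose-reduction row. By MedDRA term, relatedness appears only in Table 3.2.15 (pemigatinib-related serious TEAEs), and action taken only in Tables 3.2.18 to 3.2.20 (pemigatinib reduction, interruption, discontinuation).

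**Columns and data.** SAP 5.2 plans a column for "pemigatinib 9 mg QD + pembrolizumab 200 mg". For causality, Protocol 9.3 says that when drugs are combined, "then the relationship to each study drug/reference therapy must be assessed".

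**The concern.** The SAP sets one definition of treatment-related and then tabulates another. For monotherapy participants the two coincide, since study treatment is pemigatinib. For combination participants they do not: an investigator may attribute an event to pembrolizumab and not to pemigatinib, and Protocol 9.3 requires that distinction to be recorded. Protocol 2.3.1 mentions "potential risks of cytokine release syndrome, pneumonitis, or myocarditis related to immune checkpoint inhibitor therapy". That passage is about the course of COVID-19 and gives no expected rate here, but it shows that partner-attributed events are conceivable.

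Safety is the study's only objective. If such an event occurred, the combination column would understate toxicity attributed to the treatment actually received, and Listing 2.7.5 would show a participant with a treatment-related AE who is counted in no relatedness row.

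Separately, in every column, non-serious related TEAEs would not be tabulated by SOC and PT, although the Protocol says that related TEAEs will be.

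**Working it through.** There is no stated figure to reproduce. The check is a count of the planned displays against the definitions.

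**Step 1: class each display in SAP 7.2.2** (Appendix A lists the matching 10 tables: 3.2.1 plus nine by term).

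| Display | Counts every TEAE, whatever drug is blamed | Pemigatinib only |
|---|---|---|
| Overall summary, 8 rows | 4: any, serious, Grade 3 or higher, fatal | 4: related, interrupted, discontinued, reduced |
| By-term summaries, 9 | 5: by SOC/PT, by PT frequency, Grade 3 or higher, serious, fatal | 4: related serious, reduction, interruption, discontinuation |

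The rows add to 4 + 4 = 8 and 5 + 4 = 9.

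**Step 2: look for what SAP 7.2.1 and Protocol 10.3.3 call for.**
- Rows or tables of TEAEs related to study treatment as a whole, or to the partner drug: 0.
- Tables of all related TEAEs by SOC and PT: 0.
- Rows or tables of interruption or discontinuation of the partner: 0.

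**Step 3: look for other displays that might fill the gap.** The exposure and dose-modification summary (SAP 6.4) and the one administration listing (2.5.1) cover pemigatinib only. Disposition (SAP 6.2) reports discontinuation of study treatment, but does not say whether stopping the partner alone counts. Listings 2.7.5 (treatment-related AEs) and 2.7.6 (AEs leading to action on study treatment) are not limited to pemigatinib.

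**Step 4: trace one event.** Take a serious Grade 3 TEAE in the combination column, attributed to pembrolizumab alone and leading to action on pembrolizumab alone.
- Counted: the any, serious and Grade 3 or higher rows; Tables 3.2.2, 3.2.3, 3.2.6 and 3.2.8; Listings 2.7.1, 2.7.2, 2.7.3 and 2.7.5; and Listing 2.7.6 if the action is recorded.
- Not counted: the relatedness row, Table 3.2.15, the action rows, and Tables 3.2.18 to 3.2.20.

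If the same event is attributed to both drugs, it enters the relatedness row and Table 3.2.15. If it also leads to action on pemigatinib, it enters the matching action row and table.

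**Step 5: check the data.** Causality is required for each drug (Protocol 9.3). Action taken is required only with respect to study treatment (same section), with no split by drug stated, and the eCRF is not provided.

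**The case against.** The strongest defence is that the objective concerns the safety of pemigatinib, so rows specific to pemigatinib are what it calls for. They are labelled as such, and Listing 2.7.5 carries a different label, so displays of different scope do not strictly contradict each other. With about 20 participants and exploratory analyses, case-level listings may tell more than percentages, and SAP 7.1 and 7.2.2 let listings replace sparse tables.

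Much of this stands. The pemigatinib rows are legitimate and should stay. It does not explain why SAP 7.2.1 promises a tabulation that no table delivers, or why the by-term related table in Protocol 10.3.3 has shrunk to serious events with no change declared. The by-term listing option in 7.2.2 applies when 10 or fewer participants appear in a planned table, and no all-related table is planned.

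Stronger readings that a reader might infer are not supported:
- *That the AE summaries count only pemigatinib-attributed events.* Half the overall rows and five of the nine by-term summaries ignore attribution.
- *That the combination column will show zero related and zero discontinued.* That requires every relevant event to be attributed to, or acted on for, the partner alone. Whether the partner can be stopped alone depends on parent protocols not provided.
- *That the cases are lost.* The listings can hold them.
- *That the understatement is 25 to 100 percentage points.* One affected participant among n moves a row from 0/n to 1/n, which is 100, 50, 33 or 25 points for an assumed n of 1, 2, 3 or 4. This reflects only the assumed denominator and says nothing about how often such events occur.

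**Conclusion.** The point holds as a mismatch between the SAP's definition and its displays, and as an undeclared departure from Protocol 10.3.3. It has two parts.

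1. In every column, the table of all related TEAEs by SOC and PT is missing. This rests on the text alone.
2. In the pemigatinib + pembrolizumab column, events attributed solely to the partner, or leading to action on the partner alone, are absent from the relatedness and action displays. This matters only if such events occur.

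The size of the second part cannot be given: the documents state neither the number of combination participants nor how often attribution is to the partner alone, and the effect may be nil. The overall rows for monotherapy are unaffected. This is a reporting fault that should be corrected before the tables are produced, and it does not invalidate the pemigatinib-specific results.

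**What to change.** In SAP 7.2.2 and Appendix A:

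- Keep all pemigatinib-specific rows and tables.
- Add to Table 3.2.1 a row for participants with any TEAE related to any study treatment and, in the combination column, a row for TEAEs related to the partner drug.
- Add a table of all TEAEs related to study treatment by SOC and PT, as Protocol 10.3.3 requires. If the sponsor decides against it, record that change in SAP 9.1.
- Extend Table 3.2.15 to serious TEAEs related to any study treatment.
- Add rows for partner interruption and discontinuation only if the eCRF records action taken for each drug. The documents do not show that it does, so check this first.
- State which drug an unresolved missing causality is assigned to. SAP 7.2.1 says only that it counts as treatment-related, which leaves the pemigatinib row undefined for combination participants.

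The relatedness additions use causality data that Protocol 9.3 already requires. The cost is SAP wording, a few rows and one table. No dose or clinical rule changes.

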8. INTERIM ANALYSES

There are no planned, formal interim analyses for this study.

9. CHANGES AND MODIFICATIONS TO THE ANALYSIS PLAN

All versions of the SAP are listed in [Table 2](#).

Table 2: Statistical Analysis Plan Versions

SAP Version	Date
Original	15 MAR 2024

9.1. Changes to Protocol-Defined Analyses

Not applicable.

9.2. Changes to the Statistical Analysis Plan

Not applicable.

APPENDIX A. PLANNED TABLES, FIGURES, AND LISTINGS

This appendix provides a list of the planned tables, figures, and listings for the clinical study report. Standard tables will follow the conventions in the Standard Safety Tables v1.13. In-text tables are identical in structure and content as appendix tables but follow a Rich Text Format.

The lists of tables, figures, and listings are to be used as guidelines. Modifications of the lists that do not otherwise affect the nature of the analysis will not warrant an amendment to the SAP.

Tables

Table No.	Title	Population	Standard
Baseline and Demographic Characteristics			
1.1 Disposition			
1.1.2	Summary of Participant Disposition	FAS	X
1.2 Demography and Baseline Characteristics			
1.2.1	Summary of Demographic Characteristics	FAS	X
Safety			
3.1 Dose Exposure			
3.1.1	Summary of Exposure and Duration of Exposure to Pemigatinib	Safety	X
3.2 Adverse Events			
3.2.1	Overall Summary of Treatment-Emergent Adverse Events	Safety	X
3.2.2	Summary of Treatment-Emergent Adverse Events by MedDRA System Organ Class and Preferred Term	Safety	X
3.2.3	Summary of Treatment-Emergent Adverse Events by MedDRA Preferred Term in Decreasing Order of Frequency	Safety	X
3.2.6	Summary of Grade 3 or Higher Treatment-Emergent Adverse Events by MedDRA System Organ Class and Preferred Term	Safety	X
3.2.8	Summary of Serious Treatment-Emergent Adverse Events by MedDRA System Organ Class and Preferred Term	Safety	X
3.2.15	Summary of Pemigatinib-Related Serious Treatment-Emergent Adverse Events by MedDRA System Organ Class and Preferred Term	Safety	X
3.2.16	Summary of Treatment-Emergent Adverse Events with a Fatal Outcome by MedDRA System Organ Class and Preferred Term	Safety	X
3.2.18	Summary of Treatment-Emergent Adverse Events Leading to Pemigatinib Dose Reduction by MedDRA System Organ Class and Preferred Term	Safety	X
3.2.19	Summary of Treatment-Emergent Adverse Events Leading to Pemigatinib Dose Interruption by MedDRA System Organ Class and Preferred Term	Safety	X
3.2.20	Summary of Treatment-Emergent Adverse Events Leading to Pemigatinib Discontinuation of Study Drug by MedDRA System Organ Class and Preferred Term	Safety	X

Listings

Listing No.	Title
2.1 Participant Disposition	
2.1.1	Participant Enrollment and Disposition Status
2.2 Protocol Deviations	
2.2.1	Protocol Deviations
2.3 Safety Analyses	
2.3.1	Analysis Populations
2.4 Demographics (Including Concomitant Medications)	
2.4.1	Demographic Characteristics
2.4.2	Prior and Concomitant Medication
2.5 Drug Compliance	
2.5.1	Study Treatment Administration - Pemigatinib
2.7 Adverse Events	
2.7.1	Adverse Events
2.7.2	Serious Adverse Events
2.7.3	Grade 3 and Higher Adverse Events
2.7.4	Fatal Adverse Events
2.7.5	Treatment-Related Adverse Events
2.7.6	Adverse Events Leading to Interruption, Reduction, or Discontinuation of Study Treatment
2.11 Eye Examinations	
2.11.1	Eye Examination
2.11.2	Optical Coherence Tomography
